## 1.0 Objectives / Specific Aims

### **Aim 1: Test a home based taVNS protocol for feasibility and efficacy in NeuroCovid patients.**

We will recruit 30 formerly COVID positive adults (ages 18-70) in order to have 24 completers. We will enroll subjects who had a definite case of COVID (were antigen positive) and are at home and are no longer in the hospital. They must also have a residual neuropsychiatric symptom(s) that started anew after COVID developed (NeuroCovid). We will refer to these subjects as 'initially neurocovid and persisting'. We will also enroll those who were asymptomatic, were tested as COVID positive, and then developed NeuroCovid symptoms shortly after their testing. We call these subjects 'initially asymptomatic with later Neurocovid'. (There are several Covid diseases which occur after the acute illness has passed, particular hypercoagulable states and thrombotic strokes and heart attacks.) Symptoms we will target include anxiety, depression, and other CNS symptoms (e.g., vertigo, anosmia, headaches, fatigue, irritability, cognitive processing, etc.). Subjects will be recruited from MUSC electronic records and local testing centers, with online phone screens, consents and ratings. This study is pioneering in being entirely online and home-based. We will provide telemedicine-based device-use support on demand. There will be two experimental groups – initial active taVNS and initial sham stimulation. Subjects will be randomly assigned to each group for a two-week in-home intervention of two hours per day for six days per week of stimulation (active or sham). After the controlled 2-week period, all participants will continue in a 2-week open label arm. Outcomes will include vital signs recorded through the device, mood ratings and a cognitive battery assessing neuropsychiatric functioning and symptoms. These online ratings will be obtained at baseline, taVNS treatment weeks 1-4, and 2-, 4-, 6-, and 8- weeks after treatment. We will also assess feasibility and tolerability. The device will collect daily subjective patient data as well as heart rate, blood pressure and respiration during the treatments.

### **Aim 2: Test whether 2 or 4 weeks of stimulation differ.**

At the end of two weeks, all subjects will receive two more weeks of intervention, with all receiving active stimulation without breaking the blind. This has two purposes. First, all subjects will eventually receive active treatment, aiding IRB approval and recruitment. Second, it will examine two versus four weeks of stimulation.

This work will provide pilot data for a subsequent clinical trial application to test at home taVNS technology for specific NeuroCovid symptoms. Importantly, the data gained on device efficacy and in-home feasibility for NeuroCovid applications can be readily applied to a number of post-COVID disabilities and rehabilitation needs (e.g., COPD and other complications treated through immunomodulatory and respiratory therapy amenable to vagal nerve action). We strongly believe this technology has great potential for treating those currently sick with or disabled by COVID. We simply don't know what is in store one year from now, but it is likely that the aftershocks of this pandemic will be the defining backdrop of the next decade. A strength of this proposal is that it will allow us to pivot in the directions of greatest need in one year with a multitude of potential therapeutic targets and benefits, once initial feasibility and efficacy of the taVNS home therapy protocol has been established. The research team is experienced and are leaders in neuromodulation research and are thus uniquely capable of successfully shepherding this pilot work into a funded clinical trial.

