## 3.0 Intervention to be studied

We will be using the Soterix Medical Handheld home based taVNS device. Our group has been using taVNS in a variety of clinical laboratory, office or ICU based studies, most of them monitored through this IRB. This is the first MUSC protocol using home based taVNS.

The Soterix device is a research device that is FDA cleared in terms of safety but is not FDA approved for any indication. More information can be found here.

<https://soterixmedical.com/research/tavns>

This IRB and most others have found that taVNS is a minimal risk device and does not require an FDA IDE.

We have attached the device specifications from the manufacturer.

- Cervical VNS is FDA approved for medication resistant epilepsy as well as medication resistant depression (Livanova). FDA pivotal trials are underway for paired cervical VNS with rehab for stroke (microtransponder). Noninvasive

cervical VNS is FDA approved for treating cluster headache (electrocore). To date there are no FDA approved indications for taVNS.

- We will use the device twice daily, six days/week for an initial 2-week double blind phase followed by an additional two weeks active open phase. Thus, subjects will get 24 or 48 actual sessions over 4 weeks. Those randomized to active during the first two weeks will get twice as much overall taVNS as those who get sham during the first two weeks (*25Hz, 500us pulse width, 60s ON, 30s OFF, 1 hr. duration per session*). Subjects will be given a training video to watch and will then have an online training session with the MUSC RA. They will be instructed how to administer the device. For the first 3 sessions at least, the RA will be online watching them do this. They will prepare a checklist of how well the subject is doing the treatment. The patient can then only administer the treatment alone if they are checked off. Treatments will be monitored online for as long as it takes for the participant to be checked off.
- Active stimulation will be in the proper location in the ear. Sham stimulation will be in the same location but there will be a small ramp up of the device, delivering stimulation for 20 seconds, and then it will be programmed to turn off, until the end of the session when it will turn on again for 20 secs.

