**10.0 Study Design / Methods**

- Please see the study timeline above. Potential subjects will be phone screened and if appropriate scheduled for a consent meeting and then baseline assessments. They will then be given the video showing how to use the device. MUSC research assistants will then ship a device (and urine pregnancy test) to subjects. They will then have a training session online with MUSC RA's. Then, for each session initially they will do this online with MUSC RA's watching and rating and assisting if needed. They will complete a checklist of how well the subject administers the device. After three sessions if the subject is competent, they will self administer the device after that if they wish. All subjects can ask to have the RA online during any and all treatments if they wish. All sessions are immediately put into the database and the MUSC RA will daily monitor this and make sure the subject has correctly performed the session with no adverse events. If a subject misses a session the RA will call and talk about this. There will be immediate questions before and after each session, as well as the weekly online battery. There are also weekly online assessments and at 4,6,8 and 12 weeks after study start.

*Procedures performed to lessen the probability or magnitude of risks.*

We are excluding subjects with strokes or who are hemodynamically unstable. All sessions will be seated or even reclined if there are problems. Initial sessions are done with the MUSC RA and Soterix staff online. All session data and heart rate are sent immediately to the database and will be checked daily by research staff.

*How all drugs and devices will be used in the research (e.g. dose, dosage form, etc.)*

The device is taVNS applied to the left or right ear at two times the amplitude for perceptual threshold. This intensity of taVNS has been

used in MUSC IRB 1 monitored studies in Parkinson's Disease, Stroke Patients, Newborns and healthy volunteers. The dose for each session is *25Hz, 500us pulse width, 60s ON, 30s OFF, 1 hr. duration.*

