## **12.0 Data Management**

All data will be stored in the Redcap database. The blind will be kept by the MUSC RA, but they will be blinded as well. Soterix will set the active or sham control from the company after being instructed by the MUSC RA about the randomization code number for that patient, but MUSC will have the unblind in terms of emergency.

Information about the participant (including their identifiable private information and/or any identifiable biospecimens) may have all of their identifiers removed and used for future research studies or distributed to other researchers for future research without additional informed consent from them or their legally authorized representative.

In rare cases, the device manufacturer, Soterix, may need access to minimal PHI (such as name, phone number and address) in the event there is a device malfunction. Well-trained MUSC staff will make every attempt to resolve any issues before putting Soterix in direct contact with the participant.

At a high-level analysis, we will compare the group changes in neuropsychiatric questionnaires in active versus sham taVNS using repeated measures ANOVA from baseline to immediately after last treatment and then as well over the 3-month follow-up.

Power analysis on primary outcome: As there is no real data yet on taVNS effects on NeuroCOVID patients, it is difficult to perform a formal power analysis. The repeated measures design in 15 active and 15 sham patients will allow us to detect differences with a large or moderate effect size to be used for calculating power and sample size for subsequent trials.

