### **16.0 Potential Benefits to Subjects or Others**

A strength of this proposal is that it will allow us to pivot in the directions of greatest need in one year with a multitude of potential therapeutic targets and benefits, once initial feasibility and efficacy of the taVNS home therapy protocol has been established. The research team is experienced and are leaders in neuromodulation research and are thus uniquely capable of successfully shepherding this pilot work into a funded clinical trial. Invasive cervical VNS is FDA approved for epilepsy and depression. Noninvasive cervical VNS is FDA approved for cluster headaches. We have seen anxiolytic and antidepressant effects of taVNS. There is legitimate prospect of benefit for NeuroCovid symptoms although this is still experimental. All subjects will get the active open treatment for weeks 2-4.

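### After the week-3 switch, sham participants can probably infer their initial allocation, yet the only named efficacy analysis carries the active-versus-sham contrast past that point

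*Combined protocol and SAP*

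**What the plan says.** Section 1.0, Aim 2 has all participants continue for two more weeks "with all receiving active stimulation without breaking the blind". Three other places describe those weeks differently:

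- Section 1.0, Aim 1: "After the controlled 2-week period, all participants will continue in a 2-week open label arm".
- Section 3.0: "initial 2-week double blind phase followed by an additional two weeks active open phase".
- Section 16.0: "All subjects will get the active open treatment for weeks 2-4".

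Section 10.0 likewise counts 24 treatments as the double-blind part and lists the next 24 separately.

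On what the participant receives, Section 3.0 sets active sessions at "60s ON, 30s OFF, 1 hr. duration per session". Section 10.0 gives the intensity as "at two times the amplitude for perceptual threshold". Sham, in Section 3.0, uses the same ear location, with a short ramp "delivering stimulation for 20 seconds, and then it will be programmed to turn off", and a second 20 seconds at the end of the session.

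The only efficacy analysis named is in Section 12.0: a repeated measures ANOVA of questionnaire change, active against sham, "from baseline to immediately after last treatment and then as well over the 3-month follow-up".

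Section 10.0 mentions questions around each session and a weekly battery. It says the questionnaires were uploaded separately, and they are not part of the document under review. No treatment guess or other check of blinding is described.

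**The concern.** Two things need to be settled. The first is who is blind to what after week 2, because the sections do not agree. The second is whether the design can deliver the blinding that Aim 2 describes. Only the sham arm has a programmed change in stimulation at the switch. A participant who notices a marked change can conclude that the first two weeks were sham; one who notices none can conclude the opposite.

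This bears on the conclusions because mood and symptom ratings are among the outcomes, and such ratings are open to expectation. If participants know or suspect their first allocation from week 3 on, a later arm difference can reflect that knowledge as well as two versus four weeks of stimulation, which is the Aim 2 question. Section 12.0 also intends the observed effects to feed the sample size of later trials, so any distortion would carry forward. An uncontaminated guess about allocation can be taken only before the switch.

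**Working it through.** **Inputs.** Two sessions a day, six days a week, two weeks per phase, one hour per session, 60 s on and 30 s off, and sham bursts of 20 s at start and end (Sections 3.0 and 10.0). Active intensity is twice perceptual threshold (Section 10.0). There are 15 participants per arm (Section 12.0) and 24 completers expected overall (Section 6.0).

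**Plan's own figure.** Sessions per phase: 2 × 6 × 2 = 24. Both phases: 2 × 24 = 48. This reproduces the 24 or 48 active sessions in Section 3.0.

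**Stimulation time per session.**
- Active: 3,600 s ÷ (60 + 30) s = 40 cycles; 40 × 60 s = 2,400 s = 40 min.
- Sham: 20 s + 20 s = 40 s.
- Ratio: 2,400 ÷ 40 = 60.

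**Over the 24 double-blind sessions.**
- Sham: 24 × 40 s = 960 s = 16 min.
- Active: 24 × 40 min = 960 min = 16 h.

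A sham participant therefore reaches week 3 after 24 sessions of 40 s each and then receives 40 min per session. An initially active participant goes from 40 min to 40 min.

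**Share of ratings after the switch.** The document gives three schedules.
- Aim 1: treatment weeks 1 to 4, then 2, 4, 6 and 8 weeks after treatment, which are study weeks 6, 8, 10 and 12. Eight post-baseline points, six of them after week 2.
- Section 4.0: 2, 3, 4, 5, 6, 8 and 12 weeks. Counted from study start, six of seven fall after week 2. Taken literally as weeks after treatment, all seven do.
- Section 10.0: weekly, plus 4, 6, 8 and 12 weeks from study start. If weekly means weeks 1 to 4 (an assumption), there are seven points (1, 2, 3, 4, 6, 8, 12), five of them after week 2.

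The count varies with the schedule, but on each of these readings most ratings follow the switch.

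**Analysis window.** Section 12.0 does not say whether the last treatment is the last double-blind session or the last open one. On the second reading the main contrast ends at week 4. On the first it ends at week 2, but the follow-up part still uses data from after the switch. No separate week-2 contrast is specified.

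**What a guess item could show.** The 95% half-width for a proportion near 50% is 1.96 × √(0.5 × 0.5 ÷ n).
- n = 15 per arm: 1.96 × √(0.25 ÷ 15) = 0.25, or 25 points.
- n = 12 per arm (24 completers, even split assumed): 1.96 × √(0.25 ÷ 12) = 0.28, or 28 points.

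At 15 per arm, 12 correct guesses give an exact 95% interval of about 52% to 96%, which excludes 50%; 11 correct do not exclude it. The item would show only gross unblinding.

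**The case against.** The strongest reply is that the Aim 2 phrase has an ordinary meaning that fits an open phase: everyone now receives active treatment, and nobody is told their first allocation. Section 12.0 uses blinding in that code-access sense when it provides for emergency unblinding. Several sections already confine the double-blind phase to weeks 1 and 2, and none makes an explicit blinded efficacy claim afterwards. Section 4.0 calls the study a pilot with largely descriptive outcomes, and Aim 2 gives a reason for the switch. This reading is fair, and it reduces the contradiction to one of wording. It does not stop participants from inferring allocation, and it does not change an ANOVA that carries the active and sham labels past the switch.

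Other parts of the defence stand, and they limit what may be said:

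- A reader might infer that the switch reveals allocation. The document does not show this. Perceptibility is inferred from the active intensity; sham amplitude and any fading of sensation over a session are not given.
- A reader might infer that no treatment guess is collected. None is described, but the uploaded questionnaires have not been seen.
- A reader might infer that every later outcome is compromised. The mechanism concerns self-ratings, and does not extend in the same way to device-recorded vital signs or cognitive tests.
- A reader might infer that the week-2 result is undermined. Ratings completed before the switch cannot be affected by it.

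**Conclusion.** The concern holds in a limited form. The document is inconsistent about blinding after week 2, and on its own settings sham participants can probably infer their initial allocation from a 60-fold rise in stimulation time per session. The arm contrast in Section 12.0 uses data from after that point: six of eight post-baseline ratings in the Aim 1 schedule, with a different count but still a majority in the others. Differences in self-rated outcomes after week 2 may therefore mix treatment duration with knowledge of allocation.

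The size of any resulting bias cannot be computed from the document. The conclusion assumes that stimulation at twice threshold is felt for a good part of the session, and that participants notice the change. It should be corrected before enrolment, because it limits what the trial can claim and a guess free of the switch cannot be obtained later. It is not an error in the double-blind phase, and it is no reason to alter the treatment schedule.

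**What to change.** 1. Reconcile Aim 1, Aim 2, Section 3.0 and Section 16.0 so that all say the same thing: after week 2 initial allocation is not disclosed, but participants may infer it.
2. In Section 12.0, name the end-of-week-2 active-versus-sham contrast as the only blinded efficacy comparison. Require its ratings to be completed before the first session after the switch. Say which session counts as the last treatment, and label arm comparisons at week 4 and in follow-up as unblinded.
3. Unless the uploaded forms already contain one, add a treatment-guess item with a confidence rating to the end-of-week-2 battery, before the switch, and report it by arm. State that it can detect only gross unblinding and that a guess may also reflect perceived benefit.

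The cost is one online question, some wording, and a weaker claim for the period after week 2. Treatment, visits and sample size are unchanged.

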## 2.0 Background

Unfortunately, Coronavirus disease of 2019 (COVID-19) can enter and directly infect the brain, creating direct neurologic and psychiatric problems. Some have coined the term 'NeuroCovid' to describe this direct CNS infection and damage and differentiate this aspect of the disease from the more widely discussed systemic pulmonary and cardiovascular effects. However, the direct effects of the virus and the subsequent individual immunologic response on the brain and related outcomes are unknown. Thus, we are also just now beginning to understand that after recovery from the acute and immediate infection, many patients are struggling with longer term CNS issues, like fatigue, anosmia, anxiety and depression. Researchers are asking "Are we facing a crashing wave of neuropsychiatric sequelae of COVID-19?" Innovative therapeutic approaches, particularly home-based, are desperately needed.

Luckily, a new neuromodulation technique (Transcutaneous Auricular Vagus Nerve Stimulation – taVNS) can directly stimulate the brain and has important anti-inflammatory and other neuromodulatory functions that likely can aid with NeuroCovid recovery. taVNS may help with the acute illness, and more importantly for the proposed work, with the long-term recovery from NeuroCovid. taVNS is a new, non-invasive neuromodulation approach combining: 1) convenience (e.g. ear clip) and potential for at home delivery; 2) tolerability, even extending to testing in neonates; and 3) direct mono-synaptic modulation of deep brain nuclei that regulate parasympathetic function. taVNS offers the ability to directly treat the brain, reducing neuroinflammation and potentially improving and facilitating recovery from a variety of COVID disorders. With the rapid clinical testing supported through this proposal, taVNS may help with the long-term recovery from COVID or NeuroCovid.

Preclinical and clinical trials show that implanted vagus nerve stimulation (VNS) may be an effective anti-inflammatory treatment and may improve outcomes in disorders with inflammation. VNS prevents septic shock and can stop anaphylactic shock. VNS activates the cholinergic anti-inflammatory pathway and targets different immune, proinflammatory, and other signaling pathways, as well as modulating heart rate and blood pressure. Cervical VNS is FDA approved to treat chronic depression and also helps with anxiety but is invasive and expensive (\$30k per device). taVNS is a home-based, less expensive, non-invasive alternative.

## 3.0 Intervention to be studied

We will be using the Soterix Medical Handheld home based taVNS device. Our group has been using taVNS in a variety of clinical laboratory, office or ICU based studies, most of them monitored through this IRB. This is the first MUSC protocol using home based taVNS.

The Soterix device is a research device that is FDA cleared in terms of safety but is not FDA approved for any indication. More information can be found here.

<https://soterixmedical.com/research/tavns>

This IRB and most others have found that taVNS is a minimal risk device and does not require an FDA IDE.

We have attached the device specifications from the manufacturer.

- Cervical VNS is FDA approved for medication resistant epilepsy as well as medication resistant depression (Livanova). FDA pivotal trials are underway for paired cervical VNS with rehab for stroke (microtransponder). Noninvasive

cervical VNS is FDA approved for treating cluster headache (electrocore). To date there are no FDA approved indications for taVNS.

- We will use the device twice daily, six days/week for an initial 2-week double blind phase followed by an additional two weeks active open phase. Thus, subjects will get 24 or 48 actual sessions over 4 weeks. Those randomized to active during the first two weeks will get twice as much overall taVNS as those who get sham during the first two weeks (*25Hz, 500us pulse width, 60s ON, 30s OFF, 1 hr. duration per session*). Subjects will be given a training video to watch and will then have an online training session with the MUSC RA. They will be instructed how to administer the device. For the first 3 sessions at least, the RA will be online watching them do this. They will prepare a checklist of how well the subject is doing the treatment. The patient can then only administer the treatment alone if they are checked off. Treatments will be monitored online for as long as it takes for the participant to be checked off.
- Active stimulation will be in the proper location in the ear. Sham stimulation will be in the same location but there will be a small ramp up of the device, delivering stimulation for 20 seconds, and then it will be programmed to turn off, until the end of the session when it will turn on again for 20 secs.

